2.0 STUDY OBJECTIVES

We plan to investigate the hypothesis that combined oral contraceptives (COCs) reduce serum relaxin levels and ligament laxity in collegiate female athletes. Though this study cannot prove causality, we will also observe if rate of ligamentous injury in female athletes is reduced among women taking COC. Our specific aims are as follows:

Aim 1: To evaluate relaxin levels in female athletes on COC or no hormonal contraceptive

Aim 2: To quantify anterior and coronal plane (varus/valgus) knee laxity between female athletes using combined oral contraceptives and those who are not using any hormonal treatment.

Aim 3: To track the rate of ACL and other ligamentous injuries (ruptures / sprains) among female athletes and determine if COCs have a protective effect.

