4.0 STUDY DESIGN AND METHODS

Data will be collected prospectively throughout participant intake and study progression. Given the personal nature of women's contraceptive preferences, we will enroll three categories of female athletes:

- (1) Women who are not on hormonal contraception and have no plan to start in the next year
- (2) Women who are not on hormonal contraception and would like to initiate study COC
- (3) Women who are currently on hormonal contraception and would like to switch to study COC

For those participants who would like to start study COC, women will be prescribed a daily oral contraceptive containing ethinyl estradiol 20mcg/norethindrone 1mg.

Women will maintain a contraceptive compliance diary via paper or Word document which they can submit to us in person or electronically. Orthopedic testing will start during the fourth menstrual/COC cycle due to delay in COC effect and theoretical cumulative protective effect of COC use. All three groups will undergo below testing to evaluate primary and secondary aims.

Serum Relaxin (Aim 1):

- Participants will have about 2ccs of blood drawn to measure serum relaxin levels at two time points:
 1. Baseline
 2. Fourth month of study participation - menstrual cycle-specific timing:
 - Participants not on COC:
 - Luteal phase of their menstrual cycle (Days 14-28)
 - This is when peak relaxin levels are noted to occur
 - Participants on COC:
 - Pill pack days 14-28
 - Women on COC have suppressed ovulation and thus no true luteal phase, but will undergo testing during the same time period

Joint Laxity (Aim 2):

- Joint laxity will be tested at two separate time points:
 1. Baseline
 2. Fourth month of study participation – synced with serum collection for relaxin level testing.
- Joint Testing:
 - Each participant's bilateral knee joint laxity will be tested using a KT-2000 arthrometer (Medmetric Corp, San Diego, CA) for anterior and posterior laxity.
 - Laxity and biomechanical testing will be done in the athletes' training room on campus.
 - To eliminate inter-rater differences in the laxity measurement, only one examiner will conduct all knee laxity measurements.

- With a passive anterior and posterior drawer test at 67N and 87N, an average displacement (mm) for three cycles will be determined.
- A Brighton score will be calculated with goniometer by a one examiner to assess generalized hypermobility at each time point.

Motion Tracking Analysis (Aim 2):

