7.0 STATISTICAL CONSIDERATIONS

7.1 Study Outcome Measures

- **Data Analysis:** Statistical analysis will be performed using SAS statistical software (SAS Institute Inc., Cary, NC, USA) with significance set at $p<0.05$. Differences in the two timepoints will be evaluated between the two groups. Multiple regression will be used to analyze rate of injury as a function of OC use (group), joint laxity, motion analysis, and serum relaxin, and additional demographic data. Post-hoc ANOVA, or non-parametric alternative, will be used to evaluate continuous variables (joint laxity, motion analysis, and serum relaxin levels) between groups.
- Serum relaxin-2 level will be measured using a Quantikine Human Relaxin-2 Immunoassay (DRL200). All samples will be run in duplicate and relaxin-2 concentrations will be calculated from the standard curve. The intra-assay and inter-assay coefficients of variation and minimum detection limit will be determined and reported.
- Joint laxity measurements will be evaluated using the KT-2000 and the Beighton Score. The KT-2000 measures anterior and posterior displacement (mm) of the tibia relative to the femur when an anterior and posterior load are applied to the tibia. The amount of tibial displacement provides information on ACL laxity. The Beighton score is screening technique for measuring generalized joint hypermobility.¹ It requires the performance of 5 maneuvers, four passive bilateral and one active unilateral performance:
 1. Passive dorsiflexion and hyperextension of the fifth MCP joint beyond 90°
 2. Passive apposition of the thumb to the flexor aspect of the forearm
 3. Passive hyperextension of the elbow beyond 10°
 4. Passive hyperextension of the knee beyond 10°
 5. Active forward flexion of the trunk with the knees fully extended so that the palms of the hands rest flat on the floor

The Beighton score is based on a 9-point scale with ≥ 4 considered hypermobile.

- Continuous measures of trunk flexion, hip adduction, and internal/external and coronal plane rotation of the knee measured during a singled-legged drop using the motion tracking equipment mentioned above in section 4.0 (Aim 2). These outcomes measures are all in angles (degrees). Increased valgus knee motion (in the coronal plane) and landing with the femur in adduction and internal rotation has been suggested to predispose athletes to injury when landing from a jump.¹⁰

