7.1 Sample Size Considerations

The primary outcome measure of this study is the rate of ligament injury. Therefore, our sample size requirements were based on this measure. Previous research indicates female athletes' risk of injury is sport dependent. In Dragoo et al.'s 2011 analysis, they report a 60% rate of ACL injury among basketball players, and a ~30% injury rate among soccer, gymnastics, and lacrosse female athletes.⁴ Whereas field hockey and volleyball had a reported 0% rate of injury. Thus, we believe it is reasonable to estimate that females not taking oral contraceptives will have an estimated 30% risk of ligament injury, which we aim to demonstrate a 20% absolute reduction to 10% risk of injury among females taking OCs. Assuming equal sizing, based on previous studies that demonstrate approximately half of female athletes are on OCs,² we estimate a total sample size of 140 will provide approximately 80% power to detect an ACL Injury rate difference of 10% (OC) versus 30% (non-OC).

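### Sport is not secured in the primary injury analysis, although the contraceptive groups are self-selected and the plan itself treats injury risk as differing sharply by sport

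*Combined protocol and SAP*

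**What the plan says.** The primary outcome is set in section 7.1 (Sample Size Considerations): "The primary outcome measure of this study is the rate of ligament injury". Aim 3 in section 2.0 is "To track the rate of ACL and other ligamentous injuries (ruptures / sprains) among female athletes" and to judge whether COCs protect.

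Groups form by preference. Section 4.0 enrols athletes who stay off hormonal contraception, those already on it who switch to the study pill, and "Women who are not on hormonal contraception and would like to initiate study COC". There is no randomisation, matching or stratification.

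The injury analysis in section 7.1 (Study Outcome Measures) reads: "Multiple regression will be used to analyze rate of injury as a function of OC use (group), joint laxity, motion analysis, and serum relaxin". The full covariate list ends: "joint laxity, motion analysis, and serum relaxin, and additional demographic data". Sport is not named as a covariate, stratum or subgroup there or anywhere else. Section 5.2 does not list it among the variables collected. It appears as an eligibility criterion in section 3.2, limited to basketball, soccer and volleyball.

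On sport and risk, the sample size section says that "risk of injury is sport dependent". Of its cited study it writes: "they report a 60% rate of ACL injury among basketball players, and a ~30% injury rate among soccer, gymnastics, and lacrosse female athletes". It continues: "Whereas field hockey and volleyball had a reported 0% rate of injury".

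**The concern.** A confounder needs two links: one to the outcome and one to the exposure. The plan asserts the first, with quoted rates running from 0% to 60% across the three sports it enrols. The second is open, because athletes choose their group and nothing in the design keeps sport mix equal. If COC users are lighter in basketball, an inert pill looks protective. If they are heavier in basketball, a real effect is hidden.

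The open-ended reference to demographic data leaves room to add sport later. It does not oblige anyone to do so, and a choice made after injuries are known would look data-driven. An analyst who ran the stated model on the variables listed in section 5.2 would leave sport out.

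**Working it through.** **1. The plan's own sample size.** Inputs from section 7.1: 30% v 10%, equal groups, significance at 0.05 (two-sided assumed), 80% power. A two-proportion calculation with continuity correction gives 72 per group, 144 in total, against the stated 140. At 70 per group, power is 79.2% with continuity correction and 81.3% by Fisher's exact test. The sizing arithmetic reproduces and is not the fault here.

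**2. False difference from sport mix alone.** Risks are the quoted 0.60 (basketball), 0.30 (soccer) and 0 (volleyball). Sport counts by group are assumptions, because the documents give none. With no COC effect:

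expected group risk = (0.60 × basketball + 0.30 × soccer + 0 × volleyball) / group size

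For example, 16/23/30 gives (9.6 + 6.9)/69 = 23.9%, and 30/23/16 gives (18.0 + 6.9)/69 = 36.1%, a false difference of 12.2 points.

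The unadjusted column is a Pearson chi-square test by exact enumeration. The stratified column is a Mantel-Haenszel test by sport (200,000 simulations).

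| COC v non-COC (basketball/soccer/volleyball) | Expected risk | False difference | False positives, unadjusted | Stratified by sport |
|---|---|---|---|---|
| 20/23/26 v 26/23/20 | 27.4% v 32.6% | 5 points | 6.5% | 5% |
| 18/23/29 v 29/23/18 | 25.3% v 34.7% | 9 points | 19% | 5% |
| 16/23/30 v 30/23/16 | 23.9% v 36.1% | 12 points | 32% | 5% |
| 14/23/33 v 33/23/14 | 21.9% v 38.1% | 16 points | 58% | 5% |

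With sport counts exactly equal (23/23/23 in each group) the unadjusted test rejects only 2.1%, so 6.5% in the first row is a rise, though small against the nominal 5%.

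**3. A regression of the planned form.** Logistic regression on group plus six covariates standing in for laxity, motion, relaxin and demographics, assumed unrelated to sport and to injury (3,000 simulations per row). Without sport, false positives are 7%, 19%, 31% and 55% for the four rows. With sport added in a Firth-penalised fit they are 3–4%.

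**4. Imbalance in the other direction.** True risk ratio 1/3 (the plan's 10% v 30%), COC users heavier in basketball:

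| COC v non-COC | Power, unadjusted | Power, stratified |
|---|---|---|
| 23/23/23 in each | 88% | 91% |
| 26/23/20 v 20/23/26 | 73% | 91% |
| 30/23/16 v 16/23/30 | 44% | 90% |

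The regression without sport against the Firth fit with sport gives 87% v 88%, 71% v 87% and 43% v 85%.

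**5. How far this depends on the assumptions.**
- Narrower sport spreads, unadjusted false positives with no COC effect:

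| Assumed risks (basketball/soccer/volleyball) | 5-point row | 9-point row | 12-point row |
|---|---|---|---|
| 30/15/0% | 5.6% | 10.4% | 15% |
| 45/30/15% | 5.5% | 8.6% | 11% |
| 40/30/20% | 5.3% | 6.7% | 8% |

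The row labels refer to the counts in step 2. The false differences shrink with the spread.
- Exchanging basketball for soccer instead of volleyball (16/30/23 v 30/16/23): 6 points and 8%, on the quoted rates.
- The 12- and 16-point rows are large imbalances: a sport-by-group chi-square test gives p = 0.014 and 0.0005. A false difference as large as the 20-point design effect needs about 11 v 35 basketball players.
- If COC choice were unrelated to sport (46 athletes per sport, 69 per group), chance alone gives a bias of at least 5 points either way in 25% of trials, at least 9 points in 3% and at least 12 points in 0.5%. Averaged over such splits, the unadjusted test still rejects about 5.1%. Chance imbalance therefore distorts the individual trial and costs precision, but does not raise the overall false-positive rate. A systematic link between sport and COC choice does raise it.

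**The case against.** The strongest reply is that only half of the confounding is documented. The plan reports no link between sport and COC choice, and without one the overall error rate stays near 5%. The quoted rates are also weak inputs. They are for ACL injury, while the primary outcome is ligament injury and Aim 3 counts sprains. The soccer figure is shared with gymnastics and lacrosse, and the volleyball figure with field hockey. The largest results combine the widest risk spread with severe imbalances. The simulated regression uses covariates unrelated to sport and injury, whereas the plan expects relaxin, laxity and landing mechanics to bear on injury, so the residual bias could differ. Section 2.0 concedes that the study cannot prove causality, and the demographic wording could take in sport.

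Most of this limits the size that can be claimed, and it stands to that extent: the larger rows are illustrations, not forecasts. It does not remove the omission. Self-selection leaves the sport–COC link uncontrolled, and these are the only sport-specific rates the plan offers. The plan itself moves from them to its assumed ligament-injury risk. Disclaiming causality does not excuse leaving out a named risk factor when Aim 3 asks about protection. An undefined covariate phrase is not prespecification.

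**Conclusion.** The concern holds and should be fixed. The omission is certain from the text: a factor the plan itself calls prognostic is neither listed for collection nor named in the primary analysis of self-selected groups.

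The size of the consequence is uncertain. It rests on assumed sport counts by group and on ACL rates standing in for ligament injury. With equal sport mixes there is no bias. With a difference of 6 basketball players the false-positive rate is close to nominal (6.5%), but the reverse imbalance costs about 15 points of power (88% to 73%). Larger imbalances do serious damage in either direction. In every case examined on the quoted rates, stratifying by sport held the false-positive rate at about 5% and power at 90% or more, with no loss when the sports were balanced.

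**What to change.** - Add sport to the variables in section 5.2.
- In section 7.1 (Study Outcome Measures), name sport in the primary injury analysis, either as a stratum (Mantel-Haenszel, or stratified Cox if time to injury is used) or as a mandatory covariate. If it is a covariate in a logistic model, specify a Firth-type penalised fit, because a sport with no events, as quoted for volleyball, would cause separation. The choice among these is secondary to naming sport.
- Report the group-by-sport counts with the primary result.

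The cost is a few sentences, written before the injury data are analysed. No visit or measurement is added, because sport is already established at eligibility screening (section 3.2).

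### Ten to fourteen secondary comparisons are tested at an unadjusted p<0.05, and no laxity measure is named to decide Aim 2

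*Combined protocol and SAP*

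**What the plan says.** Section 7.1 (Sample Size Considerations) names the rate of ligament injury as the primary outcome. Section 2.0, however, states the study's hypothesis in terms of relaxin and ligament laxity, and describes injury as something that will also be observed.

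For the continuous outcomes, Section 7.1 (Study Outcome Measures) sets significance at p<0.05 and says "Post-hoc ANOVA, or non-parametric alternative, will be used to evaluate continuous variables (joint laxity, motion analysis, and serum relaxin levels) between groups". It adds "Differences in the two timepoints will be evaluated between the two groups", which does not settle whether the comparison is of change or of month-4 values. It mentions no multiplicity adjustment and does not rank the outcomes.

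The measures themselves are in Section 4.0:

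- KT-2000: "bilateral knee joint laxity will be tested using a KT-2000 arthrometer", and "With a passive anterior and posterior drawer test at 67N and 87N, an average displacement (mm) for three cycles will be determined". How the two knees are combined is not stated.
- A Beighton hypermobility score.
- Four landing angles: trunk flexion, hip adduction, internal/external knee rotation and coronal-plane knee rotation.
- Serum relaxin.

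Aim 2 reads "To quantify anterior and coronal plane (varus/valgus) knee laxity". It names no load, knee or single measure. It does not mention posterior displacement, although Section 4.0 places posterior testing under its Aim 2 laxity heading.

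**The concern.** The hypothesis that COCs reduce ligament laxity has no single test attached to it. Laxity can be read from either direction of displacement, either load, either knee or the Beighton score, and every reading uses the same threshold. One significant result among these could be reported as confirming the hypothesis, with no way to tell whether that measure was chosen before or after the results were known. A posterior result could be offered for Aim 2, because Section 7.1 says that tibial displacement informs on ACL laxity without separating the directions.

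The silence on knees matters in a second way. If both knees of each athlete were entered as separate rows in an ordinary ANOVA, which assumes independent observations, the standard errors for laxity would be too small.

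**Working it through.** The protocol gives no familywise error figure to reproduce. Its one quantitative claim, a total of 140 for about 80% power at 10% versus 30%, concerns the injury outcome. It does reproduce (72 per arm, 144 in total, with continuity correction; 79.2% power at 70 per arm with that correction) and is not affected by this point.

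**Count of comparisons.** I assume one comparison per measure between two groups, as Section 7.1 describes, and one value per landing angle.

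- Knees averaged: KT-2000 2 directions × 2 loads = 4; Beighton 1; angles 4; relaxin 1. Total 10.
- Knees tested separately: KT-2000 2 × 2 × 2 = 8; Beighton 1; angles 4; relaxin 1. Total 14.

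Testing both change and month-4 values on the 14 would give 28. Section 4.0 also says "we will enroll three categories of female athletes"; comparing those categories separately would add more.

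**Chance of at least one p<0.05 in either direction, no true effect, tests independent.** Formula: 1 − 0.95^k.

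- k = 10: 1 − 0.95^10 = 40.1%.
- k = 14: 1 − 0.95^14 = 51.2%, with 14 × 0.05 = 0.70 false positives expected.

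**Allowing for correlation.** The protocol gives no correlations, so these are assumptions: the two loads 0.8 to 0.95, the two knees 0.4 to 0.8, the two directions 0.1 to 0.5, Beighton with KT-2000 0.1 to 0.3, among the angles 0.1 to 0.4, relaxin unrelated to the rest. Simulating correlated normal test statistics (400,000 draws per setting) gives:

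- 14 tests: 38% to 46%.
- 10 tests: 33% to 37%.

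As a harsher check, one common correlation among all 14 gives 47% at 0.2, 35% at 0.5 and 25% at 0.7.

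**Only the direction that would support the hypothesis.** Landing angles are not in the Section 2.0 hypothesis, and an increase would contradict it. Each two-sided test then contributes 2.5%: 1 − 0.975^k.

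- Relaxin + Beighton + 4 KT-2000, k = 6: 1 − 0.975^6 = 14.1%.
- Relaxin + Beighton + 8 KT-2000, k = 10: 1 − 0.975^10 = 22.4%.
- Dropping posterior displacement, k = 4 or 6: 9.6% or 14.1%.

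These assume independence; positive correlation lowers them. The reference value for one test is 2.5%.

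**The alternative in which knees are pooled as rows.** With between-knee correlation ρ, the true variance of a group mean is (1 + ρ) times what the ANOVA assumes, so the actual type I error is 2 × [1 − Φ(1.96/√(1 + ρ))].

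- ρ = 0.5 (assumed): 1.96/√1.5 = 1.600, giving 11.0%.
- ρ = 0.8 (assumed): 1.96/√1.8 = 1.461, giving 14.4%.

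This applies to each of 4 KT-2000 tests. It is an alternative to the 14-test count, not an addition to it.

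**The case against.** The strongest reply is that this family is secondary. Injury rate is named as primary, Section 7.1 itself calls these ANOVAs post-hoc, and Aim 1 already has its one measure. That stands as a limit on scope: the gap is Aim 2 and the unadjusted secondary family, not the primary analysis. It does not remove the point, because Section 2.0 rests the hypothesis on these outcomes and Section 7.1 applies p<0.05 to them without labelling them exploratory.

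A reader might infer three stronger things that the documents do not support.

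- That there are at least 14 comparisons. Fourteen requires each knee to be tested separately; Section 4.0 leaves this open, and averaging gives 10.
- That a false COC effect is about as likely as not. The 51% figure assumes 14 independent tests, yet the same knee at two loads and two knees of one athlete are plainly related. It also counts results in the wrong direction and landing angles outside the hypothesis.
- That the plan analyses knees as independent units. It says no such thing; it only fails to exclude it.

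Posterior displacement cannot simply be called outside Aim 2 either. Section 2.0 omits it and Section 4.0 includes it, which is an inconsistency to settle.

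**Conclusion.** The point holds as a gap in the secondary analysis. The plan tests 10 to 14 measures at an unadjusted p<0.05 and does not say which laxity measure decides Aim 2 or how the two knees are handled. The familywise false-positive risk is 40% to 51% under independence and roughly 33% to 46% under the correlations assumed here. For a false result that would appear to support the hypothesis, about 14% to 22% under independence is the more relevant range. The 11% to 14% error per KT-2000 test arises only if knees are pooled as rows. All the correlations are assumptions, but the either-direction risk stayed well above 5% under the structured correlations and was still 25% at a common correlation of 0.7. The sponsor should fix this; it does not undermine the primary outcome or the sample size calculation.

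**What to change.** In Section 7.1 (Study Outcome Measures), before outcome data are examined:

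- Keep injury rate as primary and serum relaxin as the Aim 1 measure.
- Name one deciding measure for Aim 2: anterior KT-2000 displacement at one pre-chosen load, averaged over the athlete's two knees, with the athlete as the unit, compared between groups as change from baseline to month 4.
- Report posterior displacement, the other load, the Beighton score and the landing angles as exploratory, with estimates and 95% confidence intervals and no significance claims.
- State that the coronal-plane part of Aim 2 is addressed only by the coronal knee angle during landing, because the KT-2000 does not measure it. That part of the aim would then be exploratory, and the text should say so openly.

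Holm's correction across the relaxin and laxity tests is optional, since they serve separate aims. Without it, two independent tests carry 1 − 0.95^2 = 9.75%; with it, the smaller p-value is tested at 0.025.

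The change needs no further data or participants. Its cost is that the other laxity and landing measures can no longer be declared significant.
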